6.2 MEASURES TO MINIMIZE BIAS: RANDOMIZATION AND BLINDING

Randomization

Randomization will be conducted for all 6 sites simultaneously by a study statistician blinded to SNF identity. The randomized allocation sequence of the SNF will determine the beginning and end dates for three phases of patient and caregiver enrollment: (1) standard of care, (2) the pre-implementation phase when staff are trained and neither patients nor caregivers are enrolled, and (3) the implementation phase when newly enrolled patients and their caregivers receive the Connect-Home intervention.

Blinding

Professional data collectors from the Carolina Survey Research Lab (CSRL) will collect data from patients and caregivers at 7, 30, and 60 days post-discharge. These data collectors will be blinded to both the study hypothesis and to treatment group assignment.

6.3 STUDY INTERVENTION COMPLIANCE

The NIH Behavior Change Consortium's "Treatment Fidelity Protocols" will be used to ensure fidelity to the intervention.⁴⁶ Fidelity will be assessed in five domains as described below.

Design: The researchers will use standardized tools (e.g., Connect-Home Toolkit, the EHR template and staff training protocols) to deliver the intervention.

Training: To prevent contamination between SNFs during the intervention phase, the researcher will train staff in individual SNFs and Connect-Home Activation RNs in individual home health care offices. A detailed training protocol will be used, specifying the researcher roles, content, participants, and time required for training activities.

Delivery: A researcher will observe staff training activities on a random schedule to assess fidelity of the trainer to the staff training protocols. The research team will develop plans to address deviations from the training protocol. A Training Contact Database will be used, in which researchers will record staff participation in training activities. Staff members will be assigned identification numbers for tracking participation.

Receipt of Treatment: Researchers will administer post-tests to all participating staff after the staff training session; additional one-to-one re-training will be provided as needed for those who score

<100%. Researchers will also use return demonstration of home visit procedures with Connect-Home Activation RNs, followed by re-training as needed until nurses demonstrate a high level of ability.

Enactment of Skills: The study team will audit medical records for intervention patients to assess fidelity to the study protocol. Protocol elements to be assessed will include the following: a) completing the Transition Plan of Care; b) convening care plan meetings; c) reviewing advance directives in the SNF; d) scheduling follow-up medical appointments; e) transmitting records to follow-up clinicians; g) completing home visits within 24 hours after discharge; h) reconciling medications in the patient's home; i) completing the home safety evaluation; and j) communicating patient status to the on-coming home health nurse. As part of enactment monitoring, the Connect-Home Activation RN will keep a log describing medication discrepancies and the patients referred for a rehabilitation therapy after discharge home. Further, the researcher will host at least one 30-minute monthly meeting, during the intervention phase in each SNF, to relay feedback and discuss findings from fidelity monitoring with SNF staff and the Connect-Home Activation RN. Finally, a researcher will observe 10% of staff as they deliver Connect-Home and, using a standard checklist, the researcher will provide feedback about enactment of the Connect-Home protocols. If in-person observations are not possible (owing to risk mitigation related to COVID-19), we will monitor enactment fidelity via Zoom-based observations of care plan meetings and/ or day of discharge teaching sessions. SNFs failing to achieve 70% of operationalized fidelity steps will undergo re-training.

7 STUDY INTERVENTION DISCONTINUATION AND PARTICIPANT DISCONTINUATION/WITHDRAWAL

7.1 DISCONTINUATION OF STUDY INTERVENTION

The study will adhere to the following stopping rules:

1. The intervention is associated with adverse effects that significantly impact the risk-benefit ratio
2. Study recruitment or retention becomes futile
3. Any new information becomes available during the trial that necessitates stopping the trial
4. Other situations occur that might warrant stopping the trial

7.2 PARTICIPANT DISCONTINUATION/WITHDRAWAL FROM THE STUDY

Subjects have the right to discontinue their participation in the Connect-Home study for any reason without penalty. The Investigator also may discontinue subjects from the study if he feels as if it is in the best interest of the subject, or if the subject is noncompliant.

Due to the inclusion criteria requiring patient and caregiver participation, if either the patient or the caregiver withdraws or is discontinued from the study, the other subject will automatically be withdrawn.

The study team will cease data collection for an individual as soon as the subject withdraws from the study. The study team will retain data collected while the subject was participating in the Connect-Home trial.

If a patient enrolled in the study does not transfer from the SNF to home (i.e., they die in the SNF or are transferred from the SNF to the hospital or to long-term care), their data will not be analyzed, and the patient and the caregiver will be withdrawn.

If a patient is discharged from the SNF to home, and then dies prior to all data being collected, the data that was collected prior to the subject's death will be retained and included in analysis. If a patient has a reported death after discharge, only the data collected prior to the date of death will be used for data collection.

If a patient is discharged from the SNF to home, and then has a hospitalization and/or re-admission to a SNF; the patient will be withdrawn from the study by research team as they are now non-compliant for data collection. The data that was collected prior to the event will be retained and included in analysis.

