4.3 END OF STUDY DEFINITION

The end of study will be when the study team completes the final enrolled participant's 60-day assessments, and all data (including the final home health care chart reviews) have been collected from all study subjects. If a subject is withdrawn from the study due to an early termination caused by hospitalization, SNF re-admission and/or death; end of study for these patients will occur on day of early termination.

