Caregiver burden is measured using the Zarit Caregiver Burden Scale. It includes 12 items on a 5-point scale. Scores range 0-48, and higher scores are associated with depression and social isolation.

This measure will be assessed at 30 and 60 days post-discharge, through telephone interview with the caregiver.

Distress Thermometer²⁸

Caregiver distress is measured using the Distress Thermometer. It includes 1 item on an 11 point scale. Scores range 0-10, with scores >4 associated with poor coping and depression.

This measure will be assessed at 30 and 60 days post-discharge, through telephone interview with the caregiver.

Number of Patient Falls with Injury and Without Injury

This assessment is self-reported by the patient; falls are defined as an "unintentional change in position resulting in a resident coming to rest on the ground or lower level."

This measure will be assessed at 30 and 60 days post discharge, through telephone interview with the patient (or with the patient's legally authorized representative, responding to survey questions as the patient's proxy in cases of patients with cognitive impairment).

MD Visit

This assessment is self-reported by the patient; it is asked in a yes/no question format.

This measure will be assessed at 30 and 60 days post discharge, through telephone interview with the patient (or with the patient's legally authorized representative, responding to survey questions as the patient's proxy in cases of patients with cognitive impairment).

Hospice Enrollment

This assessment is self-reported by the patient; it is asked in a yes/no question format.

This measure will be assessed at 30 and 60 days post discharge, through telephone interview with the patient (or with the patient's legally authorized representative, responding to survey questions as the patient's proxy in cases of patients with cognitive impairment).

Home Health Care Use

This assessment is reported by the nurses and rehabilitation therapists of the patient, as a count of the number of days in home health care.

This measure will be assessed at 30 and 60 days post discharge, through telephone interview with the nurses or rehabilitation therapists.

Hospital Readmissions

This assessment is self-reported by the patient; it is a count of hospital readmissions, either acute or observational stays after SNF discharge.

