This measure will be assessed at 30 and 60 days post discharge, through telephone interview with the patient (or with the patient's legally authorized representative, responding to survey questions as the patient's proxy in cases of patients with cognitive impairment).

Emergency Department Use

This assessment is self-reported by the patient; it is a count of emergency department visits without a hospital stay after SNF discharge.

This measure will be assessed at 30 and 60 days post discharge, through telephone interview with the patient (or with the patient's legally authorized representative, responding to survey questions as the patient's proxy in cases of patients with cognitive impairment).

Death Report by Caregiver

This assessment is self-reported by the caregiver regarding patient death after SNF discharge.

This measure will be assessed at 30 and 60 days post discharge, through telephone interview with the caregiver.

Co-variate assessments will be collected in-person and from the medical record. For some caregivers, co-variate data can be collected by phone. Co-variate data are as follows:

- Patient Data collected in person:
 - Study of Osteopathic Fractures Index ¹⁰⁹, measuring frailty of the patient
 - ENRICH Social Support Inventory ¹¹⁰, measuring social support of the patient
- Patient data collected with SNF chart abstraction:
 - Demographics
 - Health insurance status
 - Medical Information
 - Depression (Minimum Data Set section D) ⁹⁴
 - Function (Minimum Data Set section GG) ⁹⁴
 - Cognitive status (Minimum Data Set section C) ^{94, 111}
 - SNF care (i.e., SNF length of stay, urgent or acute treatment while in the SNF)
 - Discharge destination
 - Charlson Comorbidity Index scores ¹¹² (calculated using the problem list in the medical record)
 - Yes or No that the SNF admission date was before the mandated pause in research activities (related to the COVID-19 pandemic)
 - History of COVID-19 diagnosis and treatment in the index hospitalization and/or in the SNF
- Caregiver data collected in-person or by phone:
 - Demographics
 - Relationship to patient
 - Employment
 - Count of days per week providing patient care
 - History of COVID-19 diagnosis and treatment

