9 STATISTICAL CONSIDERATIONS

9.1 STATISTICAL HYPOTHESES

Specific aims of this research study include:

1. Evaluate the efficacy of Connect-Home to improve SNF patient and caregiver preparedness for care at home.
 - a. Hypothesis 1a: Compared to patients enrolled in control periods, Connect-Home patients will experience greater preparedness for discharge (primary outcome, measured with the CTM-15), assessed 7 days after discharge home
 - b. Hypothesis 1b: Compared to caregivers of patients enrolled in control periods, Connect-Home caregivers will experience greater preparedness for caregiving (primary outcome, measured with the Preparedness for Caregiving Scale), assessed 7 days after discharge home.
2. Evaluate the efficacy of Connect-Home to improve SNF patient and caregiver outcomes after discharge home.
 - a. Hypothesis 2a: Compared to patients enrolled in control periods, Connect-Home patients will experience better quality of life and function (secondary outcomes), and fewer falls requiring medical assistance (exploratory), measured 30 and 60 days after discharge home
 - b. Hypothesis 2b: Compared to caregivers from control periods, Connect-Home caregivers will experience less burden and caregiver distress (secondary outcomes), measured 30 and 60 days after discharge home
3. Evaluate the efficacy of Connect-Home to prevent acute care use up to 60 days after SNF discharge.
 - a. Hypothesis 3a: Compared to patients enrolled in control periods, Connect-Home patients will have fewer days of acute care use (composite of emergency department and hospital use) (secondary outcome) and more hospice enrollment (exploratory), measured 30 and 60 days after discharge home

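### The dyad rule in 7.2 ends follow-up of a willing remaining member and, read literally, also stops the caregiver's day-30 and day-60 calls once the patient is readmitted

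*Combined protocol and SAP*

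**What the plan says.** Section 7.2 ties the two members of a dyad together: "if either the patient or the caregiver withdraws or is discontinued from the study, the other subject will automatically be withdrawn". The reason given is that the entry criteria require both to take part. The next paragraph adds: "The study team will cease data collection for an individual as soon as the subject withdraws from the study". Data already collected are kept.

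The investigator may discontinue a subject on grounds of "best interest of the subject, or if the subject is noncompliant". Later in 7.2, when a patient who has gone home is hospitalized or re-admitted to a SNF, "the patient will be withdrawn from the study by research team as they are now non-compliant for data collection". Section 4.3 refers to subjects "withdrawn from the study due to an early termination caused by hospitalization, SNF re-admission and/or death" and ends the study for these patients on that day.

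Caregiver burden (Zarit scale) and distress (Distress Thermometer) are collected only at days 30 and 60, by telephone with the caregiver (1.2, 8.1). They carry Hypothesis 2b: "Connect-Home caregivers will experience less burden and caregiver distress (secondary outcomes), measured 30 and 60 days after discharge home". Section 9.4.1 does not impute missing outcomes. Sections 9.4.2 and 9.4.3 model patient and caregiver outcomes separately.

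**The concern.** There are two parts, and they differ in how firmly the text supports them.

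The explicit part is that a person who is willing to go on and can be reached by telephone is removed because the other member left. An entry criterion explains why both must enrol. It does not explain why one person's own outcomes should stop being collected, and no model in the plan needs an intact dyad. If the exit comes before day 7, the remaining member's primary outcome is lost as well. The documents give no rate for such exits.

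The second part is an inference. If a readmitted patient counts as withdrawn or discontinued, the dyad sentence removes the caregiver too. Whether a burden or distress score exists would then depend on the patient's readmission, which happens after allocation and which Hypothesis 3a expects the intervention to make less frequent through fewer days of acute care. Missingness could differ between control and intervention periods, and caregivers of readmitted patients plausibly differ in burden from the rest. A caregiver withdrawn before day 30 has no earlier score on either scale, so the repeated-measures model in 9.4.3 has nothing from that person to use.

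**Working it through.** **How the text leads to caregiver withdrawal**

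1. Noncompliance is a ground for discontinuation (7.2).
2. A patient readmitted after going home is withdrawn as non-compliant (7.2).
3. Withdrawal or discontinuation of either member withdraws the other automatically (7.2).
4. Data collection stops at withdrawal (7.2).

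Taken literally, steps 1 to 4 end the caregiver's calls. No passage exempts caregivers of readmitted patients.

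**What points the other way**

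- For patients who never go home, 7.2 names both patient and caregiver as withdrawn. The readmission paragraph names only the patient, and 4.3 likewise speaks of patients.
- Section 8.1 schedules a death report at days 30 and 60: "This assessment is self-reported by the caregiver regarding patient death after SNF discharge". That presupposes contact with the caregiver after the patient's exit.

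**A conflict that stands on either reading**

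Section 8.1 collects hospital readmissions from the patient at days 30 and 60: "it is a count of hospital readmissions, either acute or observational stays after SNF discharge". Section 9.4.3 models cumulative acute-care days at both times. Yet 7.2 withdraws the patient at a hospitalization and 4.3 ends the study that day. Section 4.3 also lists death as a cause of withdrawal, while the death report needs the caregiver to be still in contact.

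**What is lost**

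| Caregiver withdrawn | Scores left for the 9.4.3 model |
|---|---|
| Before the day-30 call | None |
| Between the day-30 and day-60 calls | Day 30 only |

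**Size**

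Inputs: 360 dyads (1.1); dropout of 23% at day 7 and 30% at day 30 (9.2); 22% of control patients with at least one day of acute care use, in the 30-day calculation (9.2).

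- Plan's own figure: 360 × (1 − 0.23) = 277.2, which reproduces the stated 277. At day 30, 360 × (1 − 0.30) = 252.
- Dyads affected = 360 × 0.22 × s, where s is the share of acute-care users who trigger withdrawal. The documents do not give s. The 22% includes ED visits without a hospital stay, which do not trigger it.

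| Assumed s | Dyads affected of 360 |
|---|---|
| 25% | 19.8 |
| 50% | 39.6 |
| 75% | 59.4 |
| 100% | 79.2 |

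- For scale, the plan's dropout grows by 277.2 − 252 = 25.2 dyads between days 7 and 30, that is 25.2/277.2 = 9.1% of those retained. If 22% applied to all retained dyads and every trigger fell after day 7, these withdrawals alone would use up that margin once s exceeded 0.091/0.22, or about 41%. The documents do not say whether the 30% already contains them.

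Two limits apply. SNF re-admissions without acute care would add to the count, and no rate is given for them. The 22% is a control-group assumption, so using it for all 360 dyads is a simplification.

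**The case against.** The strongest reply is that the authors named both members when they meant both. The non-transfer paragraph does so; the readmission paragraph and 4.3 do not; and the caregiver death report makes sense only if caregivers stay in contact. This stands as far as it goes. A reader might infer that the protocol plainly withdraws every caregiver of a readmitted patient, and the documents do not support that. They do contain a general sentence with the word automatically and no exemption, so staff could reasonably stop the calls.

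It can also be said that the dyad is the unit of enrolment, and that for cognitively impaired patients the caregiver is both legal representative and proxy respondent. That is a fair reason for an exception in those dyads. It does not justify the rule for all others.

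Three further inferences are tempting and should not be drawn:

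- **Reduced power.** The 30% allowance may already include these losses, and no loss of the stated 89% primary power or of secondary power is shown.
- **Bias towards Connect-Home.** The documents give no basis for a direction or a size.
- **A breach of intention to treat.** Section 9.3 governs the condition under which people are analysed. The withdrawal rule does not contradict it; it governs whether there is an outcome to analyse.

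Finally, leaving outcomes unimputed is not in itself a fault. The mixed model still uses a day-30 score when day 60 is missing.

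**Conclusion.** The point holds in two grades. The automatic withdrawal of a willing remaining member is explicit, discards outcomes that could be collected, and serves no need of the analysis. Its extension to caregivers of readmitted patients follows from a literal reading, but the text is ambiguous and must be settled. On that reading, missing caregiver scores for Hypothesis 2b depend on a post-allocation event that the intervention targets.

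The effect is mainly on secondary caregiver outcomes. The range of about 20 to 79 of 360 dyads rests on two assumptions: that 22% applies to every dyad, and that 25% to 100% of acute-care users trigger withdrawal. It is an illustration of scale and not an estimate from the documents. The change is worth making because it is cheap and the calls are already scheduled.

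**What to change.** For dyads in which the patient has gone home, replace the dyad sentence in 7.2 with:

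> *When one member withdraws or is discontinued, the other is invited to continue, and his or her own scheduled 7-, 30- and 60-day assessments are collected.*

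Leave the screen-failure rule (5.3) and the non-transfer rule (7.2) unchanged. Add two exceptions:

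- The patient's participation ends if the withdrawing caregiver is the legally authorized representative and proxy, and no consent basis or respondent remains.
- Information about a patient who has withdrawn consent is not collected from the caregiver unless consent permits it.

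Then:

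- State in 7.2 that a caregiver's own follow-up continues after the patient's hospitalization or SNF re-admission.
- State in 9.4.3 whether burden and distress scores obtained during a readmission, or after the patient's death, enter the comparison. Section 7.2 limits use to data from before a death but does not say whether this covers the caregiver's own scores.
- Reconcile the termination rules in 7.2 and 4.3 with the day-30 and day-60 readmission counts and death reports in 8.1 and the acute-care days in 9.4.3.

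Costs: a protocol and consent amendment; some dyads with data from one member only, which the separate models allow; and little gained where the withdrawing caregiver is the proxy. There is also a design risk. In a one-way stepped wedge, a change adopted after enrolment has begun gives fuller follow-up to later, mostly intervention, periods. The date of the change should be recorded and its influence checked in a sensitivity analysis.

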4 STUDY DESIGN

4.1 OVERALL DESIGN

Connect-Home is a stepped-wedge cluster randomized trial (SW-CRT) to test the Connect-Home intervention against standard discharge planning (control), using both patients discharged to home (N=360) and their caregivers (N=360) in 6 SNFs.⁴⁴ In this design, SNFs will be randomly allocated to one of six sequences of time-periods defined by the month at which a SNF begins the control condition and, after a two-month staff training period, the time-period (or "step") that begins the Connect-Home protocol condition (Figure 2).⁴⁵ Thus, all SNFs will contribute data for both the Connect-Home intervention and standard care in a uni-directional crossover design at the cluster (SNF) level; a patient and their caregiver receives either standard discharge planning or Connect-Home consistent with the treatment condition of the SNF at the time of the patient's enrollment.

Randomization will be conducted for all sites simultaneously by a study statistician blinded to SNF identity. The randomized allocation sequence of the SNF will determine the beginning and end dates for three phases of patient and caregiver enrollment: (1) standard care, (2) the pre-implementation phase when staff are trained and neither patients nor caregivers are enrolled, and (3) the implementation phase when newly enrolled patients and their caregivers receive Connect-Home.

Patients and caregivers will be enrolled on a rolling basis at the rate of 4-5 dyads per month anytime during the control or intervention period. There will be three phases of patient and caregiver enrollment: (1) standard of care (indicated by blue boxes in Figure 2), (2) the pre-implementation phase when staff are trained and neither patients nor caregivers are enrolled (indicated by orange boxes in Figure 2), and (3) the implementation phase when newly enrolled patients and their caregivers receive the Connect-Home intervention (indicated by green boxes in Figure 2).

Figure 2. Stepped Wedge Design with treatment condition by month for 6 SNFs enrolling 4 patients and their caregivers per month (N= 360 patients and 360 caregivers)

SNF	Period = 1 month																					
	1	2	3	4	5	6	7	8	9	10	11	12	13	14	15	16	17	18	19	20	21	22
1	4	4	4	4	4			4	4	4	4	4	4	4	4	4						
2		4	4	4	4	4	4			4	4	4	4	4	4	4	4	4				
3			4	4	4	4	4	4	4			4	4	4	4	4	4	4	4	4		
4				4	4	4	4	4	4	4	4			4	4	4	4	4	4	4	4	
5					4	4	4	4	4	4	4	4	4			4	4	4	4	4	4	4
6						4	4	4	4	4	4	4	4	4	4			4	4	4	4	4

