5.3 SCREEN FAILURES

Subjects who discontinue following consent (i.e., post in-person questionnaires at recruitment) but prior to receiving the Connect-Home intervention or control will be considered screen failures. No additional data will be collected from the time of screen failure, but data collected prior to screen failure and reason for screen failure will be kept.

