- In Step 1, SNF nurses, rehabilitation therapists, and social workers will develop a Transition Plan of Care and prepare the patient and caregiver to manage the patient's serious illness and functional needs at home. Staff also will use American Geriatrics Society recommendations for self-care at home in the context of the COVID-19 pandemic (when applicable).

- In Step 2, the Connect-Home Activation RN (employed in the collaborating home health agency) will visit the patient and caregiver at home within 24 hours of discharge; the nurse will work with them to activate the Transition Plan of Care at home. Nurses also will use American geriatrics Society recommendations for self-care at home in the context of the COVID-19 pandemic (when applicable).

Process	Patient/Caregiver Services and Supports	Day
Step 1. Transitional care in the SNF ²⁷	
Set goals for home-based care (45 minutes)
 
Consulting with the patient/caregiver, SNF staff use the EHR template to describe goals in the patient’s Transition Plan of Care, targeting 6 key care needs (home safety and level of assistance, advance care planning, symptom management, medication reconciliation, function and activity and coordination of follow-up medical care). Staff will use American Geriatrics Society recommendations for self-care at home in the context of the COVID-19 pandemic (when applicable).
 
 • Nurses create goals for planned treatments at home, and responses to emerging symptoms or other health changes at home • Rehabilitation therapists create goals for mobility, transfers and self-care at home. • Social worker creates goals for caregiver support, follow-up care & discharge disposition. 	2 - 17

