9.3 POPULATIONS FOR ANALYSES

An intent to treat analysis will be used in which all patients/caregivers are included in the analysis according to their treatment allocation at enrollment, regardless of whether they receive the full intervention.

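### Sections 5.3 and 7.2 remove consented participants from both conditions after allocation, so the analysis that will be run is not the intent-to-treat analysis stated in 9.3

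*Combined protocol and SAP*

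**What the plan says.** Four parts of the combined protocol and SAP bear on who is analyzed.

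- **9.3 (populations):** the analysis is called intent to treat, and "all patients/caregivers are included in the analysis according to their treatment allocation at enrollment, regardless of whether they receive the full intervention".
- **4.1 (design):** a dyad's condition is fixed when it enrolls. Care is "consistent with the treatment condition of the SNF at the time of the patient's enrollment".
- **7.2 (withdrawal):** if an enrolled patient dies in the SNF, or leaves it for hospital or long-term care, "their data will not be analyzed, and the patient and the caregiver will be withdrawn". The same section lets the investigator discontinue a participant, for non-compliance among other reasons, and withdraws the second member of a dyad whenever the first leaves.
- **5.3 (screen failures):** people who stop after consent "but prior to receiving the Connect-Home intervention or control will be considered screen failures". For them, "No additional data will be collected from the time of screen failure". Data already collected are kept, but their use in the analysis is not stated.

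Two further rules matter. Section 5.4 recruits patients for whom discharge home is an expectation, within 10 days of admission. Section 9.4.1 does not impute missing outcomes.

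**The concern.** An intent-to-treat analysis keeps people in the condition assigned to them whatever happens next. Here two post-enrollment events decide who can be analyzed: where the patient goes on leaving the SNF, and whether the participant stops before treatment begins. No section reconciles these rules with 9.3 or defines a modified analysis set.

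Two things are at stake. First, two analysts reading the plan could build different primary datasets, and a result from the filtered one would be reported as intent to treat. Second, if removal differs between control and intervention periods and is related to preparedness, the CTM-15 and PCS comparisons are no longer protected by the allocation. Section 6.2 states blinding only for the outcome data collectors, not for those who recruit or who classify a screen failure. The primary models in 9.4.2 adjust for age, gender, race and, for CTM-15, respondent source. Frailty, comorbidity and function are collected, but they are not named in those primary models.

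**Working it through.** **1. Timing of the removals.**

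| Step | Section | Consequence |
|---|---|---|
| Condition set at enrollment | 4.1 | Allocation is complete for that dyad |
| Discharge home only expected at recruitment | 5.4 | Destination is a post-allocation event |
| Non-home discharge: not analyzed, dyad withdrawn | 7.2 | Post-allocation exclusion, stated outright |
| Stopping before treatment: screen failure, data collection ends | 5.3 | Post-allocation loss of the day-7 outcome |
| Missing outcomes not imputed | 9.4.1 | The 5.3 group cannot enter the day-7 model |

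Section 7.2 excludes from analysis in terms. Section 5.3 does so only in effect, through the missing outcome. Both apply to intervention and control.

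**2. The plan's own sample size.** From 9.2: 360 enrolled, 23% dropout, 277 analyzed. 360 x (1 - 0.23) = 277.2, so the figure reproduces. The plan does not say whether the 23% includes the removals under 5.3 and 7.2.

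**3. Power if the removals are additional.** The SD of log CTM-15 is not given, so the 89% cannot be checked directly. I used the plan's model (SNF random intercept, SNF-by-period random effect, linear trend, ICCs 0.10 and 0.05, effect 0.15, two-sided 5%), the Figure 2 layout as extracted, and a normal approximation. The SD that returns 89% at 277 is about 0.194. Holding it fixed, N = 360 x (1 - e) x 0.77, and the enrollment needed to keep 277 is 277 / 0.77 / (1 - e). The rates e are assumed.

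| Extra exclusion e | N analyzed | Power | Enrollment needed |
|---|---|---|---|
| 0% | 277 | 89% | 360 |
| 5% | 263 | 88% | 379 |
| 10% | 249 | 87% | 400 |
| 15% | 236 | 85% | 424 |
| 20% | 222 | 84% | 450 |

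If the 23% already covers these removals, the first row applies. Power is a minor issue either way.

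**4. What selection could do.** Let e1 and e0 be the removal rates in intervention and control, and g1 and g0 the mean log CTM-15 of those retained minus that of those removed. The retained mean exceeds the full mean by e x g, so

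shift = e1 x g1 - e0 x g0.

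- Equal rates and equal gaps: shift = 0.
- Assumed e0 = 10%, e1 = 15%, both gaps 0.15: (0.15 - 0.10) x 0.15 = 0.0075, or 5% of the 0.15 target.
- Assumed e0 = 10%, e1 = 20%, both gaps 0.50: (0.20 - 0.10) x 0.50 = 0.05, or 33% of the target.
- Swap the two rates and each shift has the same size with the opposite sign.

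None of these rates or gaps is in the documents. The formula shows what would have to differ, not what will.

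**The case against.** The strongest reply is that the trial is about people who go home. The synopsis and 4.1 describe patients discharged to home, and both primary outcomes are taken seven days after that discharge. A patient who goes elsewhere has no primary outcome as defined. This stands: restricting to home discharges may be a defensible target. It is still not the population in 9.3, and it needs its own name.

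Second, the label in 5.3 hardly changes who is analyzed, because 7.2 stops data collection for anyone who withdraws, in either condition and at any stage. This stands for people who withdraw their own consent. It does not cover those discontinued by the investigator, or the willing partner of someone who left. They could still be called at day 7.

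Third, part of the remedy exists already: reasons for screen failure are kept, discharge destination is abstracted, and dropout reasons go into the annual report (10.1.5). None of these defines the analysis set.

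Two stronger readings are tempting. A reader might infer that only the intervention group is filtered, since usual discharge planning could be under way at consent while Step 1 goal-setting falls on days 2-17. But 5.3 names control as well, 7.2 applies to both conditions, and no section says when usual planning begins. A reader might also infer that Connect-Home changes who goes home, because in Step 1 the "Social worker creates goals for caregiver support, follow-up care & discharge disposition". One planning task does not show an effect on destination. If more marginal patients were sent home, the bias could run against Connect-Home.

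**Conclusion.** The inconsistency is real and should be fixed. The rules in 5.3 and 7.2 take consented people out after allocation, so the planned analysis does not have the intent-to-treat property that 9.3 claims. This rests on the text alone.

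Selection bias is possible, not demonstrated. A figure for bias in favor of Connect-Home, obtained by assuming removals in the intervention periods only, would not be supported: it sets control removals to zero against the wording of both rules, and the documents give neither removal rates nor score gaps. Size and direction remain unknown. The power cost is about 1 to 5 percentage points for an assumed 5-20% extra exclusion, conditional on the back-solved SD, and nil if the 23% already includes these removals.

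**What to change.** 1. **Sections 5.3 and 7.2, follow-up.** Limit screen failure to people found ineligible or not consented. Make the 7-, 30- and 60-day calls to every consented participant whose patient goes home and who has not personally withdrawn consent. Include those discontinued by the investigator and the partners of people who withdrew. Analyze them in their enrollment condition.
2. **Sections 7.2 and 9.3, analysis set.** Replace the intent-to-treat wording for efficacy with a named set: 'enrolled and discharged home, by condition at enrollment'. Report every post-consent exclusion, and non-home discharge, by condition. Compare non-home discharge using the logit mixed model already planned in 9.4.3, with SNFs as fixed effects if events are sparse. If it differs, add a sensitivity analysis weighted for the probability of discharge home, estimated from baseline covariates.
3. **Section 9.2, sample size.** State whether the 23% dropout includes these exclusions.

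The cost is protocol wording, a few more calls and one extra model, plus the weighted analysis if it is triggered. Discharge destination and the covariates are already collected. The estimate may be slightly diluted by people who did not receive the full intervention, which is what an intent-to-treat analysis intends. The follow-up change matters most while enrollment is open, since a day-7 call that was not made cannot be recovered.
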